## 1. Abbreviations

AE	Adverse Events
ADE	Adverse Device Events
CI	Confidence Interval
CIP	Clinical Investigation Plan
CRF	Clinical Record Form/Case Report Form
CRO	Clinical Research Organisation
DHMA	Danish Health and Medicines Authority
ECG	ElectroCardioGraphy
EDDI	Epileptic seizure Detector Designed by IctalCare
EEG	ElectroEnchephaloGraphy
EMG	ElectroMyoGraphy
EMU	Epilepsy Monitoring Unit
FDR	False Detection Rate
GTC	Generalized Tonic-Clonic
IFU	Instruction For Use
IRIS	IctalCare Research Investigation System
MD	Medical Doctor
REC	Research Ethics Committee
SAE	Serious Adverse Event
SADE	Serious Adverse Device Effects
sEMG	surface EMG
SNR	Signal-to-Noise Ratio
SW	SoftWare
USADE	Unanticipated Serious Adverse Device Effects

## 2. General

## 2.1 Introduction

Epilepsy is the second most common acute neurological disorder, with a world-wide prevalence of 0.8-1.0% [1]. A third of the patients are medically refractory [2-4], and where no other treatment (surgery, ketogenic diet) has an effect, an automatic detection alarm would be of great help to the patients and their relatives.

In a quantitative study we found biomarkers for the differences of epileptic and physiologic tonic activity [5]. Based on the findings a generalized tonic-clonic (GTC) seizure detection algorithm was designed based on conventional surface ElectroMyoGraphy (surface EMG / sEMG), which proved to work with a sensitivity of 100% and a false detection rate (FDR) of 0.04/h in a second study [6]. In a third study this algorithm was implemented into a wireless sEMG device (IctalCare Research Investigation System (IRIS)) and tested on patients. It proved to show equally well results for the sensitivity, and the FDR was decreased to 0/h [7].

A second generation of the wireless sEMG device (EDDI) is designed and this clinical study will serve as a confirmative study, to prove the reliability (based on sensitivity and FDR) of the product.

## 3. Overall synopsis of the clinical investigation

## 3.1 Background

Epilepsy is a common serious neurological condition with a prevalence of 0.8-1.0%. People with epilepsy find it helpful to consider safety aids or equipment that might help them with day-to-day life. For example, an alarm that can alert family or friends when someone has a seizure, or a safety pillow if they have seizures when asleep. IctalCare developed EDDI (Epileptic seizure Detector Designed by IctalCare), a wireless alarm (in the form of a plaster) that is able to detect GTC seizures in epileptic patients.

In a clinical investigation (DK007-ME) an algorithm, which made it possible to detect GTC seizures, was developed. It was first tested in IRIS a predecessor for EDDI in a second clinical investigation (DK006-ME). IRIS was used on 13 epileptic patients to measure sEMG. GTC seizures were confirmed by the gold standard (video monitoring and ElectroEncephaloGraphy (EEG) recordings) for four patients, and the algorithm proved efficient. No SADE, nor SAEs, nor device deficiencies that might have led to a SAE were reported.

#### **3.1.1 Hypothesis**

From our previous results on the same type of data (sEMG) we expect that the sensitivity and FDR of this study will be comparable. The differences lie within the newer version of the device (EDDI) measuring the sEMG signal. The software is the same as used in IRIS, and most of the hardware is aswell the same. The electrode is different, but clinical tests have shown that the newer electrode provides a signal-to-noise ratio (SNR) which is equally good or better compared to the older version of the electrode (used with IRIS in DK006-ME).

#### 3.2 Purpose

The purpose of this clinical investigation is to test the reliability of the epileptic GTC seizure detection device EDDI. Furthermore the study should also evaluate whether the device is able to differentiate the convulsive epileptic (GTC) seizures from non-epileptic convulsive seizures.

EDDI will be tested on patients with epilepsy, who are expected to experience GTC seizures (or nonepileptic psychogenic seizures) during their admission to one of the epilepsy monitoring units (EMUs) participating in the study. These (patients with epileptic GTC seizures) constitute the patient group for which EDDI is intended.

In the investigation the only change from a normal admission in the EMU is the addition of the EDDI, which is placed on the outer side on one of the upper arms of the patient, as shown in the Instruction For Use (IFU) of the device.

It is validated, that this addition will not add any risks to the participating patients.

#### 3.3 Test design

The current clinical investigation will use the algorithm developed in the DK007-ME investigation. It will be conducted as a double-blinded clinical investigation assessing the sensitivity and specificity of EDDI, an epilepsy alarm, for detection of GTC seizures in patients with epilepsy. The double-blinded part will be between the physicians annotating when GTC seizures exists based on EEG and video, the gold standard, and the epilepsy alarm, which annotates when GTC seizures exist based on the EMG signal.

Patients will be hospitalized at a specialized epilepsy center either to investigate suspected epilepsy or to improve their epilepsy diagnosis and treatment. During their hospitalization patients will at least be monitored by the gold standard: video monitoring and EEG.

In this investigation, approximately 20 patients with GTC seizures will be needed, along with approximately 10 patients with PNES. This means that probably 70-80 patients in total will be included and equipped with an EDDI, after providing their informed consent. The Epilepsy Alarm should be placed on one of the upper arms (the outer side of biceps) as shown in the IFU for the device. It will need to be replaced with a new electrode every 24 hours. After a maximum of 4 days, the patient will be discharged from the hospital, thus the investigation is finalized. During the investigation sEMG signals will be recorded through the EDDI, the seizure detections by the algorithm will be electronically annotated to compare against the times annotated by the staff based alone on the gold standard. The detections of the EDDI will be hidden for the clinical personnel until the end of the admission of the patient. When the admission of the patient has ended, the clinical personnel will remove an SD-card from the A-Unit, and ship it off to the device manufacturer, who will extract the seizure times, and sent them to the principal investigator.

The investigation will be conducted in accordance with the ethical principles that have their origin in the Declaration of Helsinki, ISO 14155 (2011) and the requirements of the local competent authorities.

#### **3.4 Objectives**

#### 3.4.1 Primary objective

• To investigate the sensitivity of EDDI's ability to detect GTC seizures.

#### 3.4.2 Secondary objectives

- To investigate the specificity of EDDI's ability to detect GTC seizures.
- To investigate reasons for possible registered false alarms.
- To investigate the latency of the seizure detection by the EDDI compared to the actual start of the GTC seizure.
- To investigate the EDDI's ability NOT to detect PNES which visually look like GTC seizures.

#### 3.5 Endpoint definitions

#### 3.5.1 Primary endpoint

**The sensitivity** of the alarms will be defined from comparing the annotated time slots for GTC seizures (by the clinical personnel) with the investigator assessment of whether a GTC seizure occurred or not within the annotated time period (GTC seizures annotated by the EDDI). For the calculation of the sensitivity, the GTC seizure onset annotated by the EDDI should lie within the onset and offset defined by the clinical personnel, when compared. The clinical personnel are blinded to the alarm (EDDI) annotations, and the EDDI is blinded to the annotations set by the physicians (based on the gold standard, EEG and video).

The period to be studied for the primary alarm effect is the entire measurements on a patient. The sensitivity is then calculated as the number of the GTC seizures (defined by the gold standard), that were detected by the EDDI (a detection is counted, when a silent alarm is annotated within the seizure

period), relative to the total amount of GTC seizures (counted based on the gold standard). When a seizure annotated by the clinical personnel is not registered by the EDDI, it should be checked whether the EDDI have been turned on, before it is reported as a false negative.

## 3.5.2 Secondary endpoints

- The specificity is calculated and evaluated indirectly as the false detection rate (the number of false detections per hour). A detection is categorized as a false detection, if it falls outside a seizure period (between start and end of a seizure, defined by the gold standard). Possible alarms during placement or removal of the device are discarded (this will only happen if the device is used wrong). All data (incl. video and EEG) are saved for each patient, which makes it possible to find the reasons for possible false alarms.
- Effect of the GTC seizure alarm in a nocturnal situation (23:00 07:00). The sensitivity will be calculated based on the data within this period of time (23:000 07:00) for each day.
- The nocturnal specificity will be calculated as the amount of false positives within the nocturnal period (23:00 07:00) for all days, with respect to the amount of hours.
- For each possible false alarm, the reason for it is checked to see if there is a reasonable explanation.
- The measure for whether the EDDI captures the PNES is calculated as the total number of PNES minus the number of captured PNES and divided by the total number of PNES. This means that a measure close to 100% ensures that the device will not alarm on PNES, and the closer the measure is to 0%, the more false alarms may come from PNES.

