#### 8.6 Data collection

#### 8.6.1 CRF data

The following information will be annotated in the CRF:

- Patient number
- Gender
- Age
- Diagnosis
- Monitoring, start and stop time
- For the seizures:
  - seizure type (Simple partial, complex partial, hypermotor, myoclonic, tonic, clonic, GTC, generalised – other than the above mentioned)
  - o for the GTC seizure and PNES:

- Date and time of start and stop of the seizure.
- Comments
- Investigation center
- AE type and description

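### The false-detection rule in Protocol 3.5.2 is not limited to GTC seizures, so read literally it can leave alarms during PNES, and possibly other seizures, out of the hourly false detection rate

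*Protocol*

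**What the plan says.** Section 3.5.2 replaces specificity by an hourly rate: "The specificity is calculated and evaluated indirectly as the false detection rate (the number of false detections per hour". It then sets the rule: "A detection is categorized as a false detection, if it falls outside a seizure period (between start and end of a seizure", with the seizure defined by the gold standard. No seizure type is named. The nocturnal rate in the same section counts false positives between 23:00 and 07:00 and has no definition of its own.

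Other parts of the protocol bear on what a seizure period means:

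- **3.4.2, objective:** "To investigate the specificity of EDDI's ability to detect GTC seizures".
- **3.5.1, primary endpoint:** for GTC seizures, "a detection is counted, when a silent alarm is annotated within the seizure" period.
- **3.5.2, last bullet, on the PNES measure:** "the closer the measure is to 0%, the more false alarms may come from PNES".
- **8.2.2, comparator:** alarms are set against the physician's reading of when GTC seizures took place.
- **8.6.1, CRF:** the form records "seizure type (Simple partial, complex partial, hypermotor, myoclonic, tonic, clonic, GTC" and a further generalised category. Start and stop times are asked only "for the GTC seizure and PNES".

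Sections 9.1 and 10.1 repeat that specificity will be calculated. Section 9.1 adds a 95% confidence interval for the FDR. Neither says which seizures, if any, exempt an alarm from being false.

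**The concern.** The device is meant to alarm on GTC seizures and nothing else. Sensitivity counts only GTC seizures. If the exemption from being false covers any seizure, an alarm during a non-GTC event drops out of both measures.

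The FDR is not a minor output. Section 2.1 rests the reliability of the device on sensitivity and FDR, and reports 0 per hour for the predecessor device. Section 7.1.3 expects comparable results here. When the expected count is close to zero, reclassifying a handful of alarms decides whether the trial reports zero. The PNES group is 10 of the 30 target patients in 9.2, so such events are part of the design. If the rule stays open, it may be settled after the alarm times are known.

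**Working it through.** **Step 1. What the wording covers.** The question is whether an alarm in each kind of event is false, under the rule as worded and under a GTC-only rule.

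| Alarm occurs during | Rule as worded | GTC-only rule |
|---|---|---|
| GTC seizure | not false | not false |
| PNES | not false (PNES are called seizures; CRF holds start and stop) | false |
| Other epileptic seizure, periods taken from the CRF | false (no times recorded, so no period exists) | false |
| Other epileptic seizure, periods taken from video-EEG | not false | false |
| No event | false | false |

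Sections 3.2, 8.3 and 10.1 all refer to PNES as seizures, so the PNES row uses the protocol's own vocabulary. The rows that differ are PNES and, depending on the data source, other epileptic seizures.

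**Step 2. Does the PNES endpoint make up for it?** That endpoint is (total PNES − captured PNES) / total PNES. It is a proportion of events. The FDR is a count per hour of observation. Alarms reported in the first are not thereby included in the second.

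**Step 3. Size.** The protocol states no expected FDR, no limit for it and no total observation time, so there is no planned figure to reproduce. Let b be alarms outside every event, x alarms inside non-GTC events, and T hours observed.

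- Literal reading: FDR = b/T
- GTC-only reading: FDR = (b + x)/T
- Difference: x/T, whatever b is

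T is an assumption built from the documents. Stays are 1 to 4 days (8.4.2). Section 8.3 limits the final evaluation to GTC and PNES patients (20 + 10 = 30 in 9.2), while 9.1 uses everyone who wore the device (about 80).

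- Shortest: 30 × 1 × 24 = 720 h
- Longest: 80 × 4 × 24 = 7,680 h

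x is also assumed:

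| x | x/T at 720 h | x/T at 7,680 h |
|---|---|---|
| 5 | 0.0069 per hour | 0.00065 per hour |
| 10 | 0.0139 per hour | 0.0013 per hour |
| 20 | 0.0278 per hour | 0.0026 per hour |

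**Step 4. Effect on the reported interval.** The exact Poisson 95% limits for k events are χ²(0.025; 2k)/(2T) and χ²(0.975; 2k+2)/(2T). Take b = 0 and T = 7,680 h.

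- Literal reading, k = 0: 0 to 0.00048 per hour
- GTC-only, x = 5, k = 5: 0.00021 to 0.00152 per hour
- GTC-only, x = 10, k = 10: 0.00062 to 0.00239 per hour

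With 10 such alarms the two intervals do not overlap. With 5 they do.

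**The case against.** The best reply is that the context already means GTC. Section 3.3 describes the gold-standard annotation as marking GTC seizures, 3.5.1 uses the same term for GTC seizures immediately before, and 8.2.2 compares alarms with GTC times only. On that reading the last bullet of 3.5.2 agrees with the rule. This is a fair account of the likely intent, and it stands as such. It does not remove the defect, because the rule itself is unqualified and neither 9.1 nor 10.1 settles it.

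Second, PNES alarms are not hidden. They have an objective, an endpoint and a planned count, expected to be 0 (10.1). That also stands. What remains open is whether they enter the hourly rate as well.

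Third, a reader might infer that every alarm in a non-GTC epileptic seizure is excluded. The documents do not support this. Judged on CRF data, such alarms fall outside every recorded period and count as false. They are exempt only if periods come from the stored video-EEG.

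A reader might also infer that the FDR is biased in the device's favour by design, on the ground that PNES and motor seizures are its likeliest false triggers. The protocol contains no figure on that and expects no PNES alarms. If none occur in any non-GTC event, x = 0 and the two readings agree.

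**Conclusion.** The point holds as an ambiguity in a stated rule, not as a demonstrated bias. Taken literally, section 3.5.2 exempts PNES alarms from the FDR, and exempts alarms in other epileptic seizures if their periods are read from video-EEG. Both the 24 h and the nocturnal rate can then be understated. That sits badly with 3.4.2, 8.2.2 and the closing bullet of 3.5.2.

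The possible understatement is x/T. For x = 5 it is between 0.0069 per hour (T = 720 h) and 0.00065 per hour (T = 7,680 h). Both x and T are assumptions, so this illustrates scale and predicts nothing. The primary endpoint and the sample size in 9.2 do not depend on the definition. It is worth correcting because the FDR is one of the two reliability measures and the correction is small.

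**What to change.** In 3.5.2, state: *A detection is false if it falls outside a gold-standard GTC seizure period.* Say that this applies to both the 24 h and the nocturnal FDR. The existing exemption for placement and removal of the device need not change.

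Report false detections in three groups: during PNES, during another epileptic seizure, and outside any event. A reader can then see the rate with and without non-GTC events.

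The cost is a short change of wording and one table, and the FDR may come out slightly less favourable. PNES times are already in the CRF. For other epileptic seizures the CRF has no times, so that group must be assigned from the video and EEG check that 10.1 already plans for each false positive.

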#### 9.2 Sample size consideration for alarm correctness

With an expected sensitivity of 95%, a sample size of at least 19 patients with epileptic GTC seizures is needed. Based on this it has been chosen to include 20 patients with epileptic GTC seizures and furthermore 10 patients with PNES. To succeed in this inclusion, it is expected that about 80 patients will be included in total.

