#### 10.1 Data analysis

The data analysis will be performed by the principal investigator. The sensitivity and specificity of the device will be calculated. Furthermore the specificity will be calculated explicitly during night time.

For each false positive the EEG and video should be checked to see if there is an explanation for the false alarming.

Also for each GTC seizure that is registered by the alarm the latency should be calculated from the onset of the tonic phase of the GTC seizure.

For the patients with PNES it should be calculated how many of the seizures are registered by the alarm. The number is expected to be 0.

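### The PNES measure has no device-on condition, so a PNES event with the EDDI off or unworn counts as a correct non-alarm

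*Protocol*

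**What the plan says.** Section 3.5.2 gives an explicit formula for the PNES measure: "calculated as the total number of PNES minus the number of captured PNES and divided by the total number of PNES". It then interprets the result: "a measure close to 100% ensures that the device will not alarm on PNES". Section 10.1 repeats the task as a count, "For the patients with PNES it should be calculated how many of the seizures are registered by the alarm", and adds "The number is expected to be 0". None of these sentences says that the EDDI must have been on or mounted during the event.

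The protocol does consider device status, but only for sensitivity. Section 3.5.1 says that when an annotated seizure was not registered, "it should be checked whether the EDDI have been turned on, before it is reported as a false negative". The observation period in the same section is also stated for the primary effect only: "The period to be studied for the primary alarm effect is the entire measurements on a patient".

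Interruptions are foreseen. Section 3.3 says of the device on the arm: "It will need to be replaced with a new electrode every 24 hours". Section 4.2 adds a daily battery change and allows the electrode to be relocated. Section 18 lists inability or unwillingness to wear the device as a ground for withdrawal. Section 9.1 sets the wearing condition per patient (Full Analysis Set), not per event. The CRF list in section 8.6.1 has monitoring start and stop times, but no EDDI on/off or wear times.

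**The concern.** For GTC seizures an alarm is the success; for PNES, silence is. A device that is off or unworn is always silent. An event in such a period says nothing about whether the algorithm separates PNES from GTC seizures, yet the formula keeps it in the denominator and credits it to the device.

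Section 3.5.1 already recognises that a device that is not running has not been tested. That check is part of the sensitivity definition and is tied to false negatives, so a silent PNES event does not trigger it. The same fact, device off and no alarm, can therefore be discounted where it would count against the device, and is scored as success where it counts in its favour.

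At stake is the one endpoint dedicated to a purpose stated in section 3.2: telling GTC seizures from non-epileptic convulsive seizures. Section 9.2 plans for "furthermore 10 patients with PNES", so a few untestable events could be a visible share of the data.

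**Working it through.** The protocol states no figure for this bias, so there is none to reproduce. The check is algebra on the stated formula, followed by assumed values.

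**Inputs**
- Formula: (total PNES − captured PNES) / total PNES (section 3.5.2).
- Expected captured PNES: 0 (section 10.1).
- Planned PNES patients: 10 (section 9.2). No number of PNES events is given.
- p = probability of an alarm on a PNES event with the EDDI on and mounted. Not in the protocol; assumed below.
- f = share of PNES events with the EDDI off or unworn. Not in the protocol; assumed below.

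**Step 1, expected value.** Only the share 1 − f of events can raise an alarm, so the expected captured share is p(1 − f).
- Measure as written: 1 − p(1 − f)
- Measure among testable events: 1 − p
- Difference: p × f, never negative

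**Step 2, boundary cases.**
- p = 0, as the plan expects: both versions give 100%. Only the number of events behind the figure differs.
- f = 1: the formula gives 100% whatever p is, while the testable-event measure is undefined.

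**Step 3, off time limited to the daily exchange.** Assume 5 to 15 minutes off per 24 hours (1,440 minutes) and PNES events spread evenly over time.
- f = 5/1,440 = 0.35% to 15/1,440 = 1.04%
- At an assumed p = 20%: 0.20 × 0.35% = 0.07 to 0.20 × 1.04% = 0.21 percentage points

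**Step 4, longer non-wear (assumed f and p).**

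| p | f | As written | Testable events only | Difference (points) |
|---|---|---|---|---|
| 10% | 10% | 91% | 90% | 1 |
| 20% | 10% | 82% | 80% | 2 |
| 20% | 30% | 86% | 80% | 6 |
| 40% | 30% | 72% | 60% | 12 |

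**Step 5, a count example (assumed counts).** Take 10 PNES events, 2 with an alarm and 3 with the device off. As written: (10 − 2)/10 = 80%. Testable events only: (7 − 2)/7 = 71.4%. With no alarms and 3 off, both give 100%, but the exact two-sided 95% lower limit is 69.2% for 10/10 and 59.0% for 7/7.

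**The case against.** The strongest case against has four parts.

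1. **It is an inference.** No sentence says that PNES events with the EDDI off count as successes. Section 3.5.2 introduces the formula as a measure of capture by the EDDI, which could be read as covering recording time only, and section 8.4.5 has the investigation run alongside the other surveillance. A statistical analysis plan could add an evaluability rule. This is fair as to intent. But the formula is fixed over the total number of PNES events, and the protocol wrote a device check for one endpoint and not for this one. A later restriction would change the stated formula.

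2. **The asymmetry is softer than it looks.** The sentence in section 3.5.1 speaks of a seizure annotated by the staff, not of a GTC seizure, and asks for a check without saying that the event is then dropped. Both observations are right. Even so, the sentence closes the sensitivity definition and concerns only events about to be called false negatives, so it does not reach a silent PNES event.

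3. **The size may be trivial.** The only routine off time described is the daily exchange, which the flow chart in section 3.5.6 puts at the same time each day, and section 18 withdraws patients who cannot or will not wear the device. This stands. A reader might infer from the 30% rows above that the bias is large; the protocol supports no such value of f. A reader might also infer that off time must raise the result, but that needs p > 0 and the plan expects no captured PNES.

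4. **Other outputs also bear on discrimination.** Section 3.5.2 treats alarms on PNES as a source of false alarms, and each false alarm is reviewed for its cause. So this measure is not the trial's only evidence on the question. That review would not, however, correct a denominator that includes untestable events.

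**Conclusion.** The point holds as a defect in the stated definition: followed as written, the PNES measure credits events that could not have tested the device. The error can only favour the device, and it equals p × f.

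The size cannot be fixed from the protocol. Under the assumptions in the working it is about 0.1 to 0.2 percentage points at p = 20% if off time is one short exchange a day. It reaches several points only with substantial non-wear together with a real tendency to alarm on PNES. If the device never alarms on PNES, the estimate is right and only the apparent number of tested events is too large.

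Two stronger conclusions that a reader might draw are not supported. The protocol does not show that discrimination will be materially overstated. The interval contrast in the last step of the working is an illustration, not a planned output: section 9.1 promises intervals for sensitivity and specificity, names none for the PNES measure, and no PNES event count is given.

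The correction is still worth making, because the bias has a known direction, the planned PNES group is small, and the protocol already applies the needed principle to GTC seizures.

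**What to change.** In sections 3.5.2 and 10.1, define the measure as

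(PNES events with the EDDI on and mounted − captured PNES events) / PNES events with the EDDI on and mounted.

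Extend the on-check of section 3.5.1 to every PNES event without an alarm, and have it cover mounting as well as power. A captured event needs no on-check, since the alarm shows that the device was running. Use the device record for on-status, as section 3.5.1 already presupposes, and the continuous video of section 8.4.2 to confirm that the device was worn. Leave PNES events with the device off or unworn out of numerator and denominator, and report their number separately.

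The cost is a wording change in two sections, one check per uncaptured PNES event with its result recorded (the CRF list in section 8.6.1 has no field for it), and a smaller denominator that may give a slightly less favourable figure.

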## 9. Statistical considerations

#### 9.1 General considerations

A one group design is chosen due to the objective of estimation of sensitivity. No hypotheses are tested, but 95% two sided confidence intervals are constructed for the measure of sensitivity and specificity.

All patients enrolled who has been wearing the device, will be included in the Full Analysis Set (FAS) which forms the basis dataset for all analyses. No subgroup analyses are planned in advance. However if the final data end up showing equally distributed amounts of seizures from both kids and adults, we may study the result in the two subgroups.

The primary endpoint, the sensitivity, will be calculated as described in section 3.5.1 along with a 95% confidence interval (CI). The expectations for sensitivity (true positive assessments) are a lower limit of the two-sided 95% CI of more than  $95\% \pm 5\%$ .

The specificity is calculated and evaluate indirectly as the false detection rate (the number of false detections per hour). This parameter will be estimated along with 95% CI.

The effect of the GTC seizure alarm in a nocturnal situation (23:00 - 07:00) is found. Both the sensitivity and specificity will be calculated based on the data within this period of time (23:00 - 07:00) for each day and analyzed similarly to the analysis of the 24h periods.

Each false alarm is evaluated based on the video data to figure out, what may have caused it.

Adverse events (AEs) are summarized descriptively by type. Please refer to section 16 for details on AE collection types.

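### Protocol section 3.5.2 reads a PNES measure near 100% as proof of no PNES alarms, but about 10 PNES patients without an alarm still allow up to 30.8% of such patients to trigger one

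*Protocol*

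**What the plan says.** Protocol section 3.4.2 sets as a secondary objective the study of the device's "ability NOT to detect PNES which visually look like GTC seizures"; section 7.1.2 repeats it. Section 3.5.2 gives the endpoint. The measure is "calculated as the total number of PNES minus the number of captured PNES and divided by the total number of PNES". The unit is the event, and there is no per-patient term. The section then interprets the result: "This means that a measure close to 100% ensures that the device will not alarm on PNES". The same sentence says that values towards 0% point to more false alarms from PNES.

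On numbers, section 9.2 states that "it has been chosen to include 20 patients with epileptic GTC seizures and furthermore 10 patients with PNES", and section 3.3 has "along with approximately 10 patients with PNES". Neither gives a precision argument for the PNES group. On the expected result, section 10.1 asks how many PNES are registered by the alarm and adds: "The number is expected to be 0".

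On intervals, section 9.1 says that "95% two sided confidence intervals are constructed for the measure of sensitivity and specificity", where specificity means false detections per hour. It does not mention the PNES measure. No section says how several PNES in one patient are handled.

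**The concern.** Section 3.2 makes telling epileptic from non-epileptic convulsive seizures part of the purpose of the investigation, and section 8.1 names it as a secondary outcome. The only rule in the protocol for reading that outcome treats an observed proportion near 100% as settling the matter. An observed proportion is an estimate, and its uncertainty depends on how many patients and events lie behind it. The sponsor expects zero captures, so the strong reading would apply to exactly the result that is foreseen.

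Pooling adds a second problem. Patients differ in how many PNES they have during an admission, and events within one patient are likely to resemble each other. A patient with many events therefore carries most of the weight, and the ratio can look good while a notable share of patients set off the alarm. At stake is a claim that the device does not alarm on PNES, made on data that could not rule out alarms in a substantial minority of such patients.

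**Working it through.** **Inputs.** 10 PNES patients (section 9.2; approximately 10 in section 3.3); expected captures 0 (section 10.1); two-sided 95% level (section 9.1). Events per patient and within-patient correlation are not given and are varied below as assumptions.

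**The plan's own figure.** The 10 PNES patients come without a derivation, so there is nothing to reproduce. The only derived number, at least 19 GTC patients at 95% expected sensitivity, follows from n = 1.96² × 0.95 × 0.05 / d² if d is assumed to be 0.10: 18.25, rounded up to 19. It says nothing about PNES.

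**Step 1: patient level, no alarms.** The exact (Clopper-Pearson) two-sided 95% upper limit for 0 of n is 1 − 0.025^(1/n).

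- n = 10: 1 − 0.025^(1/10) = 0.3085, or 30.8%
- n = 9: 33.6%
- n = 12: 26.5%

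Other methods for 0 of 10 give 25.9% (exact, one-sided 95%), 27.8% (Wilson) and 21.7% (Jeffreys). None is near zero.

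**Step 2: how often a clean result would arise anyway.** If a share p of PNES patients truly triggers an alarm, the chance of 0 in 10 is (1 − p)^10.

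- p = 10%: 34.9%
- p = 20%: 10.7%
- p = 30%: 2.8%

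**Step 3: event level, no captures.** Assume 10 patients with m events each and within-patient correlation ρ. The effective number of events is 10m / (1 + (m − 1)ρ), put into the formula of step 1.

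| Events in total | ρ = 0 | ρ = 0.3 | ρ = 0.5 | ρ = 1 |
|---|---|---|---|---|
| 20 (m = 2) | 16.8% | 21.3% | 24.2% | 30.8% |
| 30 (m = 3) | 11.6% | 17.9% | 21.8% | 30.8% |
| 50 (m = 5) | 7.1% | 15.0% | 19.9% | 30.8% |

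The event-level limit therefore runs from 7.1% to 30.8% over these assumptions, and the protocol does not say where in that range it would lie.

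**Step 4: dominance of one patient (assumed example).** One patient has 21 events and no alarm. Nine patients have one event each, and three of these trigger an alarm. The measure is (30 − 3) / 30 = 90%, while 3 of 10 patients (30%) had an alarm.

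**The case against.** The strongest reply is that the sentence in section 3.5.2 only explains the direction of the scale: high is good, low is bad. Section 9.1 states that no hypotheses are tested, and no threshold or success rule hangs on the PNES measure. This stands as a reason to treat the point as one of interpretation on a descriptive secondary endpoint. It does not rescue the wording, which goes beyond direction and says what a high value guarantees.

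A second reply is that an interval for a secondary measure can be left to the SAP. That is right. The silence of section 9.1 on the PNES measure is not itself the finding.

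A third reply concerns units: 30.8% refers to patients, while the endpoint counts events. This also stands. A reader might infer that a measure of 100% has a lower limit of about 69% (100 − 30.8). The documents do not support that: 69% belongs to the share of patients without an alarm, and the limit for the event ratio depends on quantities that the protocol does not give.

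A reader might also infer that non-convulsive PNES pad the denominator and inflate the measure, because section 3.5.2 speaks of all PNES and the seizure-type list in section 8.6.1 has no PNES entry. The documents do not bear this out. Sections 3.2 and 8.3 use PNES for non-epileptic convulsive seizures, and section 8.6.1 asks for the start and stop of each PNES, so the events can be identified and counted. No share of non-convulsive events is given, so no size can be put on such an inflation.

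**Conclusion.** The point holds in a limited form. Section 3.5.2 draws a conclusion that the planned data cannot carry. With no alarm in 10 PNES patients, the exact two-sided 95% upper limit for the share of PNES patients with an alarm is 30.8%, and it moves between 33.6% and 26.5% for 9 to 12 patients. This treats patients as independent and assumes that about 10 are in fact obtained. For events, the limit is 16.8% to 7.1% under an assumed 20 to 50 independent events and rises to 30.8% under full within-patient correlation with equal event counts. The pooled ratio can also be dominated by one patient.

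The measure remains computable and useful as a description. The primary sensitivity estimate is not affected.

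**What to change.** In section 3.5.2, replace the assurance with wording that calls the measure an estimate of the share of PNES events without an alarm, to be read with its interval.

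Add a patient-level result: the number of PNES patients with at least one alarm over all PNES patients, with an exact 95% interval. Keep the event ratio beside it, with an interval that allows for clustering by patient, and report the number of events per patient. If no event is captured, a cluster bootstrap or robust variance gives an interval of zero width. The plan should then state that the patient-level exact limit is the one quoted.

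Optionally, repeat in section 3.5.2 that PNES means the convulsive, GTC-like events of sections 3.4.2 and 8.3.

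The data already planned suffice, and the cost is a few lines of text and analysis. The downside is that the PNES claim becomes weaker. A tighter statement would need more patients: with no alarms, an upper limit of at most 10% takes ln 0.025 / ln 0.90 = 35.01, so 36 patients.
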